6.2.3 Incidence rate analysis

Due to the different length of active treatment (placebo-controlled and OLE) period in early start versus late start subjects, FAIR (defined in Section 6.1) tables will be used for following AE analyses for the active treatment (placebo-controlled and OLE) period (presented by OLE treatment group):

1. AEs by system organ class and preferred term sorted by decreasing frequency
2. AEs by system organ class, high level group term and preferred term
3. AEs by preferred term
4. Severe or very severe AEs by system organ class and preferred term
5. Severe or very severe AEs by preferred term
6. Related AEs by system organ class and preferred term
7. SAEs by system organ class and preferred term
8. SAEs by preferred term
9. Related SAEs by system organ class and preferred term

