1 OVERVIEW OF THE STUDY

1.1 Study Design

The study design schematic is presented in [Figure 1](#).

Figure 1: Study Design Schematic

This is a randomized, double-blind, placebo-controlled, parallel-group study to evaluate the efficacy and safety of intravenously (IV) administered BIIB092 in participants with progressive supranuclear palsy (PSP) with an open-label extension.

Overall study design: The study design schematic is presented in [Figure 1](#). The study will consist of a 52-week double-blind treatment period, which will be followed by a long-term open label extension period for follow up. Participants will be randomized to receive BIIB092 or placebo. Approximately 459 participants in total will be randomized in a 2:1 ratio to receive BIIB092 or placebo (306 participants active or 153 placebo). In the double-blind treatment period of the study, participants will be dosed approximately once every 4 weeks (Q4W) for approximately 48 weeks (up to a total of 13 times). At Week 52, participants completing the double-blind treatment period may choose to continue into the open-label extension period of this study, in which, all participants will receive BIIB092. Participants will be dosed approximately once- every 4 weeks throughout the duration of the open-label extension period. The duration of the open-label extension will vary depending on the date of enrollment of the participant in the study. The study is expected to continue until BIIB092 is commercially available, the development program is terminated, or the study is terminated at the discretion of the sponsor, whichever comes first.

Study visits: Study visits will be conducted approximately every 4 weeks. Study drug will be administered and safety, efficacy, and other assessments will be performed. The study will generally be conducted on an outpatient basis unless some procedures would be better performed on an inpatient basis based on the needs of the participant. Participants will be observed and monitored by study personnel for approximately 2 hours after the end of an infusion. Participants with ongoing AEs or serious AEs (SAEs) will remain at the site or be sent to an inpatient monitoring facility until the Investigator has determined that these events have resolved or do not require inpatient monitoring.

Study assessments:

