3 GENERAL CONSIDERATIONS

3.1 General Methods

This statistical analysis plan (SAP) is for the purpose of the interim analysis which will use data collected in the placebo-controlled (PC) and open label extension (OLE) periods once all subjects have completed the PC period. It covers the analyses for the OLE portion of the study and analyses across both the PC and the OLE periods. The analysis for the PC period is documented in a separate 251PP301 placebo-controlled SAP. The analyses of selected exploratory endpoints may be documented separately. Since the objectives and endpoints given in Section 2 are taken directly from the protocol which covers both PC and OLE periods, only analyses relevant to the OLE

period which will have sufficient data at the time of the interim analysis will be presented in this SAP.

Summary tables will be presented using descriptive summary statistics. For continuous variables, summary statistics will generally include: number of subjects with data, mean, standard deviation, median, 25% percentile, 75% percentile, minimum and maximum. For categorical variables, this will generally include: number of subjects randomized or dosed, number with data, and the percent of those with data in each category.

Unless otherwise specified, change from baseline will be defined as post-baseline value minus baseline value. See Section 3.3 for the definition of baseline.

Unless stated otherwise, all statistical tests will be 2-sided with statistical significance level of 0.05.

The statistical software, SAS® will be used for all summaries and analyses.

The health care region used in the analysis (referred as region in this SAP) is defined as:

- US: United States
- Non-US: Australia, Austria, Canada, France, Germany, Greece, Italy, Russian, Spain, United Kingdom, Japan and Korea

The term “subject” is the equivalent to “participant” used in the protocol.

This OLE period analysis plan does not include listings since they are provided in the placebo-controlled period analysis (please refer to the 251PP301 placebo-controlled SAP). These listings will include all data in the placebo-controlled and OLE periods (all data in the study), with an indicator of the study period (screening, placebo-controlled, or OLE) for each record to indicate when the event occurred.

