5.3 Considerations for interim analysis

For the interim analysis, the efficacy analysis in the OLE period will only focus on the primary and key secondary efficacy endpoints:

- 28-item PSPRS total score and 15-item PSPRS total score,
- MDS-UPDRS Part II, CGI-C, PSP cognitive composite battery, and PSP-QoL.

For the primary endpoint PSPRS, the following analyses will also be conducted:

- By-visit shift from baseline analysis and the by-visit categorical summary for each individual item in the 28-item PSPRS will be presented. The same analyses will be performed for each item of the 15-item PSPRS.
- The change from baseline in each of the 6 subscales of 28-item PSPRS will be summarized by visit, analyzed by MMRM and plotted over time. The same analysis will be applied to the 3 subscales of 15-item PSPRS (gait/limb, ocular motor, and bulbar).

Because too few patients will have reached Week 100 at the time of interim analysis database lock, the CSF PD analysis and the efficacy MRI analysis will not be conducted.

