6.1.2 Analysis period and analysis displays

The analysis period will be specified for each output. Analysis periods in this SAP are:

- OLE period – for AE analyses
- active treatment (placebo-controlled and OLE) period - for all safety analyses

Safety data will be summarized by OLE treatment group (BIIB092 early start, BIIB092 late start, and in addition BIIB092 total).

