6.1.4 Incidence, incidence proportion and incidence rate

- Incidence and incidence proportion will be provided in incidence proportion tables. Incidence is defined as the number of subjects who experienced an event. Incidence proportion is defined as the number of subjects who experienced an event divided by total number of subjects in the analysis population, i.e., percentage. Each subject will be counted only once within each category.

- Incidence and incidence rate will be provided in incidence rate tables. Two different kinds of incidence rate tables will be provided as appropriate for different analyses. Definitions are provided below.
 - Follow-up adjusted incidence rate (FAIR) – defined as the number of subjects with an event divided by the total follow-up time among the subjects in the analysis population (e.g., incidence rate per 100 subject-years). The total follow-up time (subject-years) is the sum of all subjects' follow-up time, where a subject's follow-up time is calculated as the number of days (inclusive) from first dose of treatment until the last day on study divided by 365.25. For active treatment period analyses, the first dose of treatment is considered the first dose received in the study period (PC or OLE) in which a subject first receives BIIB092. Each subject will be counted only once within each category.
 - Exposure-adjusted incidence rate (EAIR) – defined as the number of subjects with an event divided by the total exposure adjusted follow-up time (i.e. total time at risk for the event) among the subjects in the analysis population (e.g., incidence rate per 100 subject-years). The exposure adjusted follow-up time (time at risk for the event) for a subject is the time from the first dose of study drug in the first BIIB092 dosing period (PC or OLE) to the initial occurrence of the event for subjects who experienced the event, and is the time from first dose of study drug in the first BIIB092 dosing period to the end of follow-up (the last day on study) for subjects who did not experience the event. The total time at risk is the sum of all subjects' time at risk. Each subject will be counted only once within each category.

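### FAIR in OLE SAP 6.2.3 still depends on follow-up length, so for common events it over-corrects the early-start versus late-start contrast; showing EAIR beside it in tables 1 to 3 is a cheap, low-priority improvement

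*SAP*

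**What the plan says.** OLE SAP 6.2.3 lists nine adverse event rate tables over the active treatment period and gives one reason for its choice of rate: "Due to the different length of active treatment (placebo-controlled and OLE) period in early start versus late start subjects, FAIR" is to be used. For early-start subjects that period covers placebo-controlled and extension data; for late-start subjects it covers extension data only (second section numbered 3.2, Analysis Period).

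OLE SAP 6.1.4 describes FAIR as "defined as the number of subjects with an event divided by the total follow-up time among the subjects in the analysis population". Each subject's follow-up is "calculated as the number of days (inclusive) from first dose of treatment until the last day on study divided by 365.25", and each subject is counted once per category. The same section defines EAIR as subjects with an event "divided by the total exposure adjusted follow-up time (i.e. total time at risk for the event"), where a subject's time stops at the first occurrence. EAIR is planned only for adverse events of special interest (6.2.4) and infusion reactions (6.2.5).

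On layout, 6.1.2 states: "Safety data will be summarized by OLE treatment group (BIIB092 early start, BIIB092 late start, and in addition BIIB092 total"). On timing, 3.1 takes the data from the placebo-controlled and "open label extension (OLE) periods once all subjects have completed the PC period". Section 1.1 adds: "The duration of the open-label extension will vary depending on the date of enrollment of the participant in the study". Section 5.3 drops two analyses for this reason: "Because too few patients will have reached Week 100 at the time of interim analysis database lock".

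**The concern.** After a first event, a subject goes on adding to the FAIR denominator and can add nothing more to the numerator. The longer the follow-up, the more of this person-time accumulates and the lower FAIR becomes, even at an unchanged hazard. FAIR is therefore still sensitive to the feature that 6.2.3 cites as the reason for using it.

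The difference in length is large at this data cut. Early-start subjects bring up to 52 weeks on drug before the extension. Few subjects will have passed 48 weeks of extension (Week 100 less Week 52). With the two groups in adjacent columns, a reader could take a lower early-start FAIR for a common term as better tolerability with longer exposure.

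**Working it through.** The plan states no event rate or FAIR value, so there is no figure of its own to reproduce.

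**Inputs from the documents.** Extra early-start time: 52 weeks, taken as 1 year (OLE SAP 1.1). Extension time: mostly below 48 weeks, 48 × 7 / 365.25 = 0.92 year (5.3). Dropout: 25% through Week 52 (1.2), carried forward as a constant rate d = -ln(0.75) = 0.288 per year, or set to zero.

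**Assumptions.** First-event hazard h is constant and equal in both groups. Extension time u is fixed at 0.25, 0.5 or 0.92 year, or spread uniformly over 0-0.92 or 0-1.5 years.

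**Formulas.** With T = 1 + u (early) or T = u (late):
- events per subject = h/(h+d) × (1 - exp(-(h+d)T))
- follow-up = (1 - exp(-dT))/d, or T if d = 0
- time at risk = (1 - exp(-(h+d)T))/(h+d)
- FAIR = events / follow-up; EAIR = events / time at risk, which reduces to h.

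For staggered entry each quantity is averaged over u before dividing.

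**Hand check** (h = 0.5, u = 0.5, no dropout).
- Early: (1 - exp(-0.75))/1.5 = 0.528/1.5 = 35.2 per 100 subject-years.
- Late: (1 - exp(-0.25))/0.5 = 0.221/0.5 = 44.2.
- FAIR ratio 0.80; EAIR is 50.0 in both groups.

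**Case nearest to the plan's timing** (h = 0.5, u uniform over 0-0.92, dropout).
- Early: 0.429 events, 1.19 years of follow-up, 0.859 years at risk.
- Late: 0.183 events, 0.42 years of follow-up, 0.366 years at risk.
- Crude ratio 0.429/0.183 = 2.34. FAIR 36.2 versus 43.4, ratio 0.83. EAIR ratio 1.00.

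The crude proportion errs in one direction and FAIR in the other.

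**Early/late FAIR ratio across cases**

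| Hazard per year | Fixed, no dropout | Fixed, dropout | 0-0.92, dropout | 0-1.5, dropout |
|---|---|---|---|---|
| 0.1 | 0.952 | 0.955-0.959 | 0.961 | 0.965 |
| 0.2 | 0.907-0.909 | 0.914-0.921 | 0.926 | 0.933 |
| 0.5 | 0.791-0.802 | 0.805-0.829 | 0.834 | 0.852 |
| 1 | 0.645-0.680 | 0.668-0.723 | 0.721 | 0.757 |
| 2 | 0.467-0.557 | 0.497-0.616 | 0.585 | 0.650 |

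At 0.05 per year the ratio is about 0.98 in every case. The 0-1.5 year column is generous: it puts about (1.5 - 0.92)/1.5, roughly 40%, of staggered entries past 48 weeks before dropout, and about 30% after it. EAIR gives 1.00 throughout.

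**Against sampling error.** With 306 early-start and 115 late-start subjects (randomised to BIIB092, and expected placebo completers), 4,000 simulations per case give a standard error of the log FAIR ratio. In the 0-0.92 year case with dropout it is 0.364, 0.206 and 0.133 at 0.2, 0.5 and 1 per year, against |ln ratio| of 0.077, 0.181 and 0.328. Over the dropout cases simulated (both staggered spreads and fixed 0.5 year), the shift is about 0.2-0.3, 0.9-1.0 and 2.5-2.9 standard errors.

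**When the hazard is not constant.** This uses a Weibull hazard common to both groups, cumulative hazard 0.5 at 1 year, u over 0-0.92, with dropout.

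| Clock and shape | FAIR ratio | EAIR ratio |
|---|---|---|
| Time on drug, 0.75 (falling) | 0.69 | 0.81 |
| Time on drug, 1.25 (rising) | 1.00 | 1.22 |
| Time on drug, 1.5 (rising) | 1.19 | 1.46 |
| Time since randomisation, 1.25 | 0.68 | 0.77 |
| Time since randomisation, 1.5 | 0.59 | 0.63 |

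Neither rate is closer to 1 for every hazard shape.

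**The case against.** **The comparison is already available elsewhere.** OLE SAP 6.2.2 plans 20 incidence-proportion tables for the extension period alone, which exclude the extra placebo-controlled year; tables 19 and 20 are by 12-week interval. Placebo-controlled SAP 6.2.2 plans matching interval tables (21 and 22). If intervals run from the first dose of each period, a reader can set the first 12 weeks on drug side by side for both groups and can also see time-varying risk. This stands and lowers the priority. The views are only partial. The extension tables compare second-year with first-year exposure, and the interval comparison spans two outputs.

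**FAIR is a legitimate choice, consistently applied.** This also stands. A reader might infer that 6.2.3 contradicts 6.1.4 or that FAIR is miscalculated. The documents do not support that: 6.1.4 states the denominator openly, allows either rate as suits the analysis, and the placebo-controlled SAP uses the same FAIR (6.1.3, 6.2.5).

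**EAIR is not reliably better.** A reader might infer that EAIR should replace FAIR. The Weibull results rule that out: with a hazard rising with time on drug, EAIR lies further from 1. If risk follows disease duration, both rates retain most of the same false contrast.

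**Few rows are affected.** Largely true. In the staggered cases with dropout, 0.5 per year means that 43-47% of early-start subjects have had the event. Few preferred terms are likely to be that frequent; system-organ-class rows may be.

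**Conclusion.** The point holds as a limited matter of interpretation. FAIR does not remove the dependence on follow-up length that 6.2.3 gives as its reason for using a rate. Under an equal, constant hazard it puts early start below late start by about 2% at 0.05 per year, 7-9% at 0.2, 15-21% at 0.5 and 24-35% at 1. These sizes rest on assumed event rates, extension lengths and dropout. Equal hazard is itself an assumption: late-start subjects begin the drug about a year later in their disease and are selected by having reached extension dosing.

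The effect is negligible for rare terms. It concerns mainly tables 1 to 3, since the other six cover severe, related or serious events, where many rows may be infrequent.

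A reader might infer that the trial's safety conclusions are biased. The documents do not support that. These tables are descriptive, and the between-group comparison in OLE SAP 5.1 is for efficacy. The primary safety comparison of BIIB092 with placebo (protocol 17.4.2) does not use these tables.

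**What to change.** In OLE SAP 6.2.3, show EAIR as already defined in 6.1.4 beside FAIR for all rows of tables 1 to 3. Do not select rows by observed rate, which would make the display data-dependent, and do not name either rate as the sole basis for comparing early with late start.

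Add one footnote to those three tables saying that:
- FAIR depends on follow-up length through person-time after the first event;
- EAIR removes this only if the hazard is roughly constant, and can be further from a ratio of 1 if the hazard rises with time on drug;
- neither rate corrects for later disease stage or for selection of late-start subjects into extension dosing;
- the 12-week-interval tables should be read alongside.

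The cost is SAP wording, a time-to-first-event derivation for each term and wider tables. The documents do not say whether the EAIR tables already planned are by preferred term, so reuse of that programming cannot be assumed. No new data or definition is needed. This is a cheap improvement of low priority.

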6.2.4 Adverse event of special interest

Immunogenicity is an AESI in the BIIB092 clinical development program. Adverse events representing potential immune/hypersensitivity reactions will be identified using customized MedDRA search criteria: Anaphylactic reaction, Angioedema, and Severe cutaneous adverse reactions via SMQ (narrow and broad) search; Eosinophilia, and Miscellaneous terms. Further details are given in Appendix 11.1.

An incidence proportion table for potential immune/hypersensitivity reactions organized by SMQ/Miscellaneous categories and by PT (for both AEs and SAEs), and similarly for potential immune/hypersensitivity reactions for subjects with and without treatment emergent positive anti-drug antibody (ADA) results will be presented for both AEs and SAEs for the OLE Period. Positive treatment emergent ADA will be based on the definition in Section 8 using the integrated placebo-controlled and open label extension data.

An exposure adjusted incident rate table will be provided for the active treatment (placebo-controlled and OLE) period.

The following analyses (incidence proportion only) will be performed for the OLE period to explore the relationship between ADAs and the safety of BIIB092:

- AEs for subjects with and without positive treatment emergent ADAs
- SAEs for subjects with and without positive treatment emergent ADAs

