11.1 Adverse event of special interest search

The following search will be performed using MedDRA 22.0.

- Anaphylactic reaction SMQ narrow and broad
- Angioedema SMQ narrow and broad
- Severe cutaneous adverse reactions SMQ narrow and broad
- Eosinophilia (PT terms: Eosinophilia; Eosinophil count increased; Allergic eosinophilia; Pulmonary eosinophilia)
- Miscellaneous terms
 - Cytokine release syndrome PT
 - Infusion related reaction PT
 - Infusion site reaction PT
 - Allergic conditions NEC HLT
 - Drug hypersensitivity PT
 - Documented hypersensitivity to administered product PT
 - Vasculitis PT
 - Systemic Lupus erythematosus PT
 - Rheumatoid arthritis PT
 - Antibody test positive PT
 - Antibody test abnormal PT
 - Antibody test PT
 - Drug specific antibody present PT
 - Neutralising antibodies PT
 - Neutralising antibodies positive PT
 - Non-neutralising antibodies positive PT

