6.2.3 Adverse event of special interest

Immunogenicity is an AESI in the BIIB092 clinical development program. Adverse events representing potential immune/hypersensitivity reactions will be identified using customized MedDRA search criteria: Anaphylactic reaction, Angioedema, and Severe cutaneous adverse reactions via SMQ (narrow and broad) search; Eosinophilia, and Miscellaneous terms. Further details are given in Appendix 11.3.

An incidence proportion table for potential immune/hypersensitivity reactions organized by SMQ/Miscellaneous categories and by PT (for both AEs and SAEs), and similarly for potential immune/hypersensitivity reactions for subjects with and without treatment emergent positive anti-drug antibody (ADA) results (as defined in Section 8) will be presented for both AEs and SAEs. A listing of potential immune/hypersensitivity reactions will be provided.

The following analyses (incidence proportion only) will be performed to explore the relationship between ADAs and the safety of BIIB092:

- AEs for subjects with and without treatment emergent positive ADAs
- SAEs for subjects with and without treatment emergent positive ADAs

In this study, additional samples for ADA, referred to as “event driven” samples, may be collected for subjects with hypersensitivity events. A listing of AEs for subjects with any event driven ADA samples will be provided.

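### The AESI search behind the hypersensitivity table split by anti-drug antibody status includes seven antibody-test terms, so that table's Miscellaneous line and any total row are partly circular if antibody results are recorded as adverse events

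*SAP*

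**What the plan says.** OLE SAP 6.2.4 names immunogenicity as an adverse event of special interest (AESI) and states: "Adverse events representing potential immune/hypersensitivity reactions will be identified using customized MedDRA search criteria". It asks for a table of these events by SMQ/Miscellaneous category and by preferred term. A similar table then covers "potential immune/hypersensitivity reactions for subjects with and without treatment emergent positive anti-drug antibody (ADA) results", for AEs and for SAEs. PC SAP 6.2.3 asks for the same split, of "immune/hypersensitivity reactions for subjects with and without treatment emergent positive anti-drug antibody (ADA) results (as defined in Section 8".

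The Miscellaneous list in OLE SAP 11.1 opens with clinical terms such as "Cytokine release syndrome PT". It closes with seven antibody entries, among them "Antibody test positive PT", "Antibody test abnormal PT", "Antibody test PT" and "Drug specific antibody present PT". The other three are Neutralising antibodies, Neutralising antibodies positive and Non-neutralising antibodies positive. PC SAP 11.3 carries the same seven.

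In both SAPs, ADA status comes from the serum assay under the rules of Section 8. Neither SAP removes the antibody terms when the AESI table is split by ADA status.

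**The concern.** The split table is there to show whether subjects who develop ADA have more immune or hypersensitivity reactions. Protocol Section 14 plans exactly this kind of comparison of safety with and without ADA. For it to inform, the event must be something other than the antibody. An adverse event coded to a drug-antibody term is the grouping variable reported a second time, and it would be expected mainly in the ADA-positive column. A subject with antibodies and no symptoms would then count towards the reactions, and the table could suggest an association where no ADA-positive subject had a clinical reaction beyond the background rate.

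**Working it through.** **Counting the terms.** The documents give no figure for this table to reproduce, so the first step is a count.

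- OLE SAP 11.1, Miscellaneous list: 16 entries (15 preferred terms and one high level term). Antibody findings: 7. Remaining without them: 16 − 7 = 9.
- PC SAP 11.3: the same 16 plus Respiratory dyskinesia, so 17. Antibody findings: 7. Remaining: 17 − 7 = 10.
- Of the seven, four concern a drug-specific, neutralising or non-neutralising antibody and overlap directly with ADA. The three antibody-test terms name no drug and could pick up unrelated tests.
- The fraction 7 of 16 describes the Miscellaneous list only. The whole search also has three SMQs (narrow and broad) and four eosinophilia preferred terms.

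**How an antibody result could enter the table.** The search runs on adverse events, not on assay results. Protocol 10.6 sends a laboratory result to the AE page if it is clinically significant, meets the SAE definition, led to interruption or discontinuation of treatment, or needed corrective therapy. Protocol Section 14 has ADA titers monitored throughout. It also asks participants who withdraw with unstable or rising titers to return for follow-up, so at least some results reach sites. The route is open, but nothing says how often it is used.

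**A comparison within the OLE SAP.** Section 6.2.5 also splits infusion reactions by ADA status. Its custom search list (Appendix 11.2) contains no antibody-test term. An antibody event could reach those tables only through its date, by the temporal-association rule.

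**Illustration for a total row.** Let r be the true reaction rate, equal in both columns, and q the share of ADA-positive subjects with an adverse event coded to an antibody term. Assume that the two are independent and that no such events occur in the other column. Then

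apparent ADA-positive rate = 1 − (1 − r)(1 − q), and ratio = apparent rate / r.

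| r (assumed) | q (assumed) | Apparent rate | Ratio |
|---|---|---|---|
| any | 0 | r | 1.0 |
| 6% | 5% | 1 − 0.94 × 0.95 = 10.7% | 1.8 |
| 6% | 20% | 1 − 0.94 × 0.80 = 24.8% | 4.1 |
| 2% | 10% | 1 − 0.98 × 0.90 = 11.8% | 5.9 |
| 5% | 10% | 1 − 0.95 × 0.90 = 14.5% | 2.9 |
| 10% | 10% | 1 − 0.90 × 0.90 = 19.0% | 1.9 |

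The documents give neither r nor q. The table shows only that a small q matters more when true reactions are rare.

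**The case against.** The strongest reply is that the overlap may never occur. ADA is not in the safety laboratory panel of either SAP, Protocol 10.6 sets conditions before a laboratory result becomes an adverse event, and nothing makes a symptom-free ADA result one. A reader might infer that every positive assay is counted as a reaction. The documents do not support that: a positive assay enters only if it is also reported as an adverse event and coded to one of these terms. Listing the terms is weak evidence that such events are expected, since Appendix 11.2 lists injection-site terms for a product given only by infusion.

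The layout also limits the damage. With rows by category and preferred term, an antibody term has its own visible row. Only the Miscellaneous line and any total row can mislead, and neither AESI section specifies a row for any reaction, whereas the infusion-reaction sections do specify such a count. The ratios above therefore apply to a total row that may not be produced.

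A reader might also infer that the overall AESI rate is wrongly inflated. That does not follow. Both SAPs declare immunogenicity itself the AESI, so antibody findings fall within the declared scope of the unsplit table.

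Finally, the comparison is a descriptive incidence proportion with no test or decision rule attached.

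All of this stands, and it limits the size and reach of the problem. It gives no reason to keep the terms in the counts of the split table: if no such event is recorded, removing them changes nothing, and if some are, removing them takes out an artefact.

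**Conclusion.** The point holds in a conditional form. In both SAPs the event definition of the ADA-split AESI table partly contains the variable that defines its columns: seven terms, at least four of them directly. If any antibody result is recorded as an adverse event, the Miscellaneous line and any total row are partly circular. The size cannot be determined from the documents and may be zero. The ratios of 1.8 and 4.1 illustrate a total row under assumed rates and do not predict the result. No efficacy conclusion or formal safety test depends on this table. The change is still worth making before the tables are run, because this is the plan's comparison of its named AESI by ADA status and the artefact can be removed in advance.

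**What to change.** In OLE SAP 6.2.4 and PC SAP 6.2.3, state that the seven antibody-result preferred terms are excluded from the category and total counts of the AESI tables split by treatment-emergent ADA, for both AEs and SAEs. In the unsplit AESI table, keep them as a separately labelled group, for example *antibody findings*. Leave the general AE and SAE tables by ADA status complete; stripping the terms from those would make them incomplete.

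The cost is one flag on seven preferred terms. The SMQ and eosinophilia parts of the search do not change, and 9 of 16 (OLE) and 10 of 17 (PC) Miscellaneous entries remain in the split tables. Nothing is lost, because Section 8 of each SAP already reports ADA incidence from the assay and the terms stay visible in the unsplit table.
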